10.2. Randomization - There is no randomization in this study

10.3. Descriptive Statistics and Exploratory Data Analysis

Initial analysis will include characterizing our consecutive patient cohort among prostate cancer risk factors including, age, PSA, race/ethnicity, prostate volume and scoring of MRI lesions. These this data will be summarized and compared to our typical clinical cohort to examine biases.

10.4. Primary Analysis

A prospective collection of correlative data including micro-ultrasound, MR imaging U/S, PSA and pathology data.

10.4.1. Analysis Population

The entire cohort

Predicting Location and Extent of Prostate Cancer using Micro-Ultrasound Imaging

10.5. Secondary Analysis

Goal will be to quantitatively co-register the micro-ultrasound data with MRI and pathology data, and apply advanced processing techniques such as machine learning or deep learning. Once an initial model is built to identify prostate cancer from micro-ultrasound, we will be able to design future studies.

10.5.1. Analysis Population

The entire consecutive series will be analyzed

10.6. Sample Size

Statistical Power for N=68:

Primary outcome: We seek to characterize the sensitivity of micro-ultrasound at detecting significant cancer, especially in comparison to the sensitivity of standard of care multiparametric MRI. With earlier published data with a sensitivity of 90%, we project to

Predicting Location and Extent of Prostate Cancer using Micro-Ultrasound Imaging

detect significant cancer at a sensitivity of 77% by PIRADS 4 and 5 at Stanford. Therefore, we propose a single micro-ultrasound cohort with a sample size of 68 subjected recruited to reach 80% power at alpha level of 0.05.

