9. MEASUREMENTS/ STATISTICAL CONSIDERATIONS

9.1. Primary outcome will be the prospective data collection of a consecutive series of biopsy and prostatectomy patients.

- PRIMARY OUTCOMES:
 - Evaluate the ability of micro-ultrasound to identify high grade prostate cancer foci (Gleason score ≥ 7) in comparison to final surgical pathology result (prostatectomy or biopsy)

9.2 Secondary outcomes will be an analysis of this data to identify or develop features that form a cancer prediction model

- SECONDARY OUTCOMES:
 - Evaluate the ability of micro-ultrasound to identify the borders of prostate cancer foci in comparison to final surgical pathology result in men after prostatectomy.
 - Evaluate the ability of micro-ultrasound to detect low grade prostate cancer foci (Gleason score 6)
 - Comparison of prostate cancer detection between micro-ultrasound and multiparametric magnetic resonance imaging (mpMRI).
 - Perform a detailed pathologic and imaging correlation between findings on micro-ultrasound, MRI and final surgical histopathology in men who undergo prostatectomy

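### Section 10.6 attaches 80% power at N=68 to a comparison with mpMRI, but 68 fits a test against a fixed 77%; paired power depends on a discordance rate the plan does not give

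*Combined protocol and SAP*

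**What the plan says.** Section 10.6 frames the primary outcome for its power statement this way: "We seek to characterize the sensitivity of micro-ultrasound at detecting significant cancer, especially in comparison to the sensitivity of standard of care multiparametric MRI". Its inputs are "With earlier published data with a sensitivity of 90"% and a projection that the site will "detect significant cancer at a sensitivity of 77% by PIRADS 4 and 5 at Stanford". It concludes: "we propose a single micro-ultrasound cohort with a sample size of 68 subjected recruited to reach 80% power at alpha level of 0.05". It gives no test, no sidedness and no rate of agreement between the two imaging methods.

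Other sections bear on this:

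- Section 9.1 sets the primary outcome as identification of Gleason ≥7 foci against pathology. Section 9.2 lists detection by micro-ultrasound versus mpMRI as a secondary outcome.
- Section 10.4 describes the primary analysis as "A prospective collection of correlative data including micro-ultrasound, MR imaging U/S, PSA and pathology data", so MRI is collected in the same single cohort.
- Section 10.1 calls the study primarily exploratory and says that no direct comparison with standard of care is intended.
- Section 3.1.1 admits men scheduled for fusion biopsy or radical prostatectomy. Significant cancer is not an entry requirement.
- Section 10.7 gives an accrual figure of 100.

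**The concern.** PI-RADS is an MRI score, so the 77% reads naturally as the MRI figure and the powered contrast as micro-ultrasound against MRI. If 68 was obtained by testing 90% against 77% as a known constant, the calculation gives MRI no sampling error. In this study both tests would be observed in the same men. The power of that comparison is driven by the cancers one test finds and the other misses, and 10.6 does not use this quantity.

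A reader of 10.6 could therefore take 68 recruited men as enough to show a 13-point gain over MRI with 80% power, which the plan has not established. Section 10.1 says the data are meant to help plan larger studies, so the basis of the stated power should be clear.

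**Working it through.** **Inputs.** From 10.6: alpha 0.05, power 80%, sensitivities 0.90 and 0.77, N = 68. Assumptions: 0.90 is micro-ultrasound and 0.77 is MRI (the wording is loose); the test is two-sided; each man contributes one result per test; and, until the last step, all 68 men have Gleason ≥7 disease.

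**Reproducing 68.** One-sample test of 0.90 against a fixed 0.77:

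n = [1.960·√(0.77·0.23) + 0.8416·√(0.90·0.10)]² / 0.13² = (0.8248 + 0.2525)² / 0.0169 = 68.67

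Power at 68: z = (0.13·√68 − 0.8248)/0.3 = 0.824, which gives 79.5%. The exact binomial version has 76.3%.

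Other standard forms do not give 68: one-sided 52.8; null 0.90 against 0.77, 52.5; continuity-corrected 76.2; arcsine 61.6; two independent groups, 127 per group.

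**The paired comparison.** Let p01 be the proportion of cancers found by MRI only, p10 = p01 + 0.13 the proportion found by micro-ultrasound only, and pd = p10 + p01. Then

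n = [1.960·√pd + 0.8416·√(pd − 0.0169)]² / 0.0169

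If misses are independent, p01 = 0.10·0.77 = 0.077, p10 = 0.90·0.23 = 0.207 and pd = 0.284, so n = (1.0445 + 0.4350)² / 0.0169 = 129.5.

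Power at 68 was computed from this normal approximation. It was also computed by enumerating the binomial number of discordant pairs and counting rejections that favour micro-ultrasound, for the asymptotic and the exact McNemar test. The values of p01 are assumptions.

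| p01 | p10 | pd | n for 80% (formula) | Power at 68: formula | Asymptotic, enumerated | Exact |
|---|---|---|---|---|---|---|
| 1% | 14% | 15% | 67.3 | 80% | 88% | 79% |
| 2% | 15% | 17% | 76.6 | 75% | 79% | 71% |
| 3% | 16% | 19% | 85.8 | 70% | 73% | 64% |
| 5% | 18% | 23% | 104.4 | 61% | 63% | 54% |
| 7.7% (independent) | 20.7% | 28.4% | 129.5 | 52% | 54% | 45% |

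A one-sided 0.05 test under independence gives 66% (asymptotic) or 58% (exact), so sidedness does not restore 80% there. With 100 cancer-bearing men and independent misses, two-sided power is 71% or 63%.

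**Men recruited versus men with disease.** Sensitivity uses only men with the disease. The share of recruits with Gleason ≥7 disease is not given. If it were 80%, 60%, 50% or 40% (assumptions), 68 recruits would yield 54, 41, 34 or 27 such men, and one-sample power would be 67%, 51%, 41% or 31%. At 50%, paired power under independence would be about 29% (formula) or 19% (exact). Recruiting 100 would yield 68 such men only if 68/100 = 68% had the disease.

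**The case against.** The strongest reply is that nothing has been miscalculated. Section 10.6 proposes a single micro-ultrasound cohort, which fits a benchmark test against 77%, and for that test 79.5% is as claimed. The mpMRI comparison is secondary and need not be powered, and 10.1 disclaims a direct comparison. Most of this stands: a reader might infer an arithmetic error in 68, and the documents do not support that. However, 10.6 never calls 77% a benchmark. It names MRI sensitivity as the comparator next to the power figure, so the disclaimer in 10.1 conflicts with 10.6 rather than curing it.

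A second reply is that the origin of 68 is not documented. This also stands. The one-sample result rounds up to 69, and the paired formula at p01 = 1% gives 67.3, which rounds up to 68. A paired origin is therefore not excluded, although it needs a discordance rate that the plan nowhere states.

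Third, it is tempting to say that the study has 54% or 45% power. That is the independent-misses case, the least favourable in the table. Misses that tend to fall in the same men raise the power, and at p01 = 2% the asymptotic paired figure (79.2%) is practically the one-sample one. The exact 45% should also be set against the exact one-sample 76.3%, not against 80%.

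Finally, no test against MRI is specified, and 10.8 rests future work on co-registration, visual feedback and ROC analysis. The documents do not show that a non-significant result would be read as no better than MRI, or that later trials would be sized from 10.6.

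**Conclusion.** The point holds as a mismatch between a stated power and the comparison it is attached to. The 80% is right for a one-sample test of 90% against a fixed 77% in 68 men with Gleason ≥7 disease. For a paired comparison with mpMRI in 68 such men who all have both tests, it is supported only if MRI alone finds about 1–2% or less of the cancers. By 3% the power is 73% (asymptotic) or 64% (exact), and it keeps falling as discordance rises.

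This rests on reading 90% as micro-ultrasound and 77% as MRI, on a two-sided test, and on assumed discordance. Both power figures fall further if some recruits lack significant cancer. Paired power also falls if some lack MRI, which is implied for fusion biopsy but not expressly required before prostatectomy. A reader might infer that about 130 men must be enrolled. The documents do not support that: the figure belongs to one assumed discordance, and 10.1 describes an exploratory study.

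**What to change.** In 10.6, name the test. State that the 80% applies only to a one-sample test of micro-ultrasound sensitivity against a fixed 77% reference, and only if 68 men with Gleason ≥7 disease are analysed. Say that 68 recruited men give less (for example, about 41% if half have such disease, an assumption). Remove the mpMRI comparison from the powered claim, and reconcile 10.6 with the disclaimer in 10.1 and the accrual figure of 100 in 10.7.

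For the comparison in 9.2, specify a paired analysis in men with Gleason ≥7 disease who have both tests: a McNemar test and a 95% confidence interval for the paired difference in sensitivity. Label it estimation only, and give its power as a range by discordance and by the number of such men.

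The cost is wording in 10.6 and 9.2 plus one table. The stated power becomes less favourable; no added enrolment is needed.

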3. PARTICIPANT SELECTION AND ENROLLMENT PROCEDURES

3.1. Inclusion Criteria

3.1.1. Patient scheduled for MR-US fusion prostate biopsy or radical prostatectomy

3.1.2. Ability to understand and the willingness to sign a written informed consent document.

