10. STATISTICAL CONSIDERATIONS

10.1. Statistical Design

This study is primarily exploratory, with the goal of collecting the initial correlative data between micro-ultrasound, conventional imaging, and pathology gold standard. As such, we are not intending to directly compare this imaging modality with standard of care, but rather to rigorously and prospectively collect this data in order to plan for larger, multi-institutional studies.

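### The 80% power behind N = 68 belongs to a test against a fixed figure, not to a comparison with MRI in the enrolled men, and Sections 10.1, 9.2 and 10.6 disagree on that comparison

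*Combined protocol and SAP*

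**What the plan says.** Section 10.6 wants the sensitivity of micro-ultrasound for significant cancer characterised, "especially in comparison to the sensitivity of standard of care multiparametric MRI". It gives two figures: 90%, attributed to published data, and a projection to "detect significant cancer at a sensitivity of 77% by PIRADS 4 and 5 at Stanford". From these it concludes "we propose a single micro-ultrasound cohort" with a "sample size of 68 subjected recruited to reach 80% power at alpha level of 0.05". It does not name the test, its sidedness, which figure is the null value, or the men from whom the 77% was obtained.

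Section 10.1 calls the study mainly exploratory and states that "we are not intending to directly compare this imaging modality with standard of care". Section 9.2 lists cancer detection by micro-ultrasound versus mpMRI as a secondary outcome, without a method.

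Entry (Section 3.1.1) is: "Patient scheduled for MR-US fusion prostate biopsy or radical prostatectomy". MRI data are collected in the cohort (Sections 8.2, 10.3 and 10.4). Section 10.4 describes the primary analysis only as data collection. Section 10.8 bases future studies on co-registration, visual review and an initial ROC analysis.

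**The concern.** The same comparison is disclaimed in one section, attached to the primary outcome in another and secondary in a third. A reader of Section 10.6 would take the 80% power to cover micro-ultrasound versus MRI. If it covers only a test against a constant, then a micro-ultrasound result above 77% could be reported as better than MRI when MRI in the same men was also above 77%. Section 10.1 says these data will be used to plan larger multi-institutional studies, so an apparent advantage that came from case mix would carry into that planning.

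**Working it through.** **Inputs.** From Section 10.6: 77%, 90%, N = 68, power 80%, alpha 0.05. Sidedness is not stated. I read the 77% as the MRI figure because PI-RADS is an MRI score, and the 90% as micro-ultrasound.

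**1. Reproducing 68.** One-sample test of a proportion, normal approximation, two-sided 0.05:

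n = [(1.960·√(0.77×0.23) + 0.842·√(0.90×0.10)) / (0.90 − 0.77)]² = [(0.8248 + 0.2525)/0.13]² = 68.7.

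Power at 68: Φ[(√68 × 0.13 − 0.8248)/0.30] = Φ(0.824) = 79.5%.

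Other forms with the same inputs do not fit: one-sided 52.8; with continuity correction 76.2; arcsine 61.6; 90% as null and 77% as alternative 52.5; two independent groups 127 per group. One caution: an exact two-sided binomial test with 90% as the null and 77% as the alternative also passes 80% at 68 (81.6%, against 79.9% at 67). The text does not settle which was used. In both, one cohort is tested against a constant, and MRI readings in the enrolled men play no part.

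**2. What exceeding 77% would show.** Assume 68 men with Gleason 7 or higher and a score test against 0.77. At 60/68, z = (0.8824 − 0.77)/√(0.77×0.23/68) = 2.20; at 59/68, z = 1.91. So 60 or more detections are needed. If micro-ultrasound and MRI have the same true sensitivity p in these men, the chance of exceeding the benchmark is P(X ≥ 60 | 68, p):

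- p = 0.77: 1.5%
- p = 0.80: 5.5%
- p = 0.85: 29%
- p = 0.90: 76%

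With fewer cancers the figures at 0.85 and 0.90 are in general lower: with 50 cancers (45 or more needed) 22% and 62%; with 40 (37 or more needed) 13% and 42%. Because counts are discrete the fall is not perfectly smooth (65 cancers, 57 or more needed: 80% at 0.90).

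**3. Could MRI sensitivity here differ from 77%?** Suppose, as an assumption, that the 77% came from unselected men and that only men with PI-RADS 3 or more reach fusion biopsy. PI-RADS 4–5 sensitivity among them would be 0.77 divided by the sensitivity of PI-RADS 3 or more. For assumed values of 95%, 90% and 85% this gives 81%, 86% and 91%. This argument does not extend to prostatectomy men.

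**4. Power of a paired comparison.** McNemar, two-sided 0.05, 68 men with Gleason 7 or higher, 90% versus 77%. Let d = 0.13, let p01 be the proportion of cancers seen by MRI only, and let ψ = d + 2·p01. Power = Φ[(√68·d − 1.960·√ψ)/√(ψ − d²)].

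- p01 = 0 (ψ = 0.13): Φ[(1.0720 − 0.7067)/0.3363] = 86%
- p01 = 0.05 (ψ = 0.23): Φ[(1.0720 − 0.9400)/0.4616] = 61%
- independent calls, p01 = 0.10×0.77 = 0.077 (ψ = 0.284): Φ[(1.0720 − 1.0445)/0.5168] = 52%. Another common form, Φ[√68·d/√(ψ − d²) − 1.960], gives 55%.

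The documents give no discordance figure, so this range is assumed.

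**The case against.** The strongest reply is that this is an exploratory single-arm study in which nothing is decided on 77%. That stands. The figure appears only in the sizing sentence, and neither Section 10.4 nor Section 10.8 sets a threshold. A reader might infer that the trial judges micro-ultrasound by whether it beats 77% and so cannot show a gain over MRI. The documents do not support that: no success rule is written, the mpMRI comparison is a listed secondary outcome, and MRI data are collected in the cohort.

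A reader might also infer that entry enriches the cohort for MRI-visible cancer, so that MRI sensitivity must exceed 77%. This too goes further than the text. The 77% is placed at Stanford without a source population; if it came from similar men, the argument largely falls away. That fusion-biopsy men were selected on MRI is a reasonable inference, not a statement in the plan. For prostatectomy men it does not follow at all: known cancer is not the same as MRI-visible cancer, and sensitivity is calculated only among men with cancer.

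Nor does the plan claim an unqualified sensitivity for the device. Section 1.1 limits it to the initial cohort, and Section 10.3 plans to compare the cohort with the usual clinical population to look for bias.

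Finally, the illustration assumes that all 68 men have Gleason 7 or higher, whereas Section 10.6 counts men recruited. None of this removes the conflict between the sections or extends the 80% power to a comparison with MRI.

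**Conclusion.** The point holds in a limited form and should be fixed. Sections 10.1, 9.2 and 10.6 conflict on whether, and at what level, micro-ultrasound is compared with MRI. The 80% power belongs to a one-sample test against a constant, most plainly 90% against 77% (68.7 against 68 stated), and not to MRI in the enrolled men. Exceeding 77% would not by itself show a gain over MRI. How misleading it could be depends on an MRI sensitivity that the documents do not give: negligible if it is 77% here (1.5%), substantial if it is 0.85 to 0.90 (29% to 76% with 68 cancers, in general less with fewer). These figures rest on an inferred score test, an assumed range and 68 men with Gleason 7 or higher.

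**What to change.** (a) In Section 10.6, name the test and say that the 80% power is for micro-ultrasound sensitivity against a fixed 77%, if that is the calculation intended. State where the 77% comes from and in which men. Remove the wording that presents this as a comparison with MRI.

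(b) Base any statement about MRI only on the paired within-man difference: micro-ultrasound minus PI-RADS 4–5 in the same men with Gleason 7 or higher, with a 95% CI. Define a detection per man, since Section 9.1 speaks of foci, and report how many men have no MRI. Show prostatectomy and biopsy men separately. Section 4.2 leaves the biopsy otherwise unchanged and describes no cores directed by micro-ultrasound, so cancers seen only on micro-ultrasound may go unsampled and biopsy verification may favour MRI.

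(c) Make Sections 10.1, 9.2 and 10.6 agree that this paired comparison is secondary and descriptive.

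Cost: protocol wording and one estimate from data already being collected. The downside is that the 80% does not carry over. With 68 cancers at 90% versus 77%, paired power is about 86% if no cancer is seen by MRI only, 61% if 5% are, and 52–55% if the calls are independent. That is a reason to report an estimate with its interval and not a test.

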10.7. Accrual estimates

This research study is looking for 100 participants and is only being conducted at Stanford.

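### Section 10.6 claims 80% power for sensitivity from 68 recruits, but the only match counts men with Gleason ≥7; test, unit and share are unstated, and 10.7 says 100

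*Combined protocol and SAP*

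**What the plan says.** - **Section 10.6 (Sample Size)** aims to characterise the sensitivity of micro-ultrasound for significant cancer, particularly against multiparametric MRI. It cites a published sensitivity of 90% and projects 77% by PI-RADS 4 and 5 at the site. It then says "we propose a single micro-ultrasound cohort with a sample size of 68 subjected recruited to reach 80% power at alpha level of 0.05". It gives no test, no sidedness, and no statement of which sensitivity is the null.
- **Section 10.7 (Accrual estimates)** says "This research study is looking for 100 participants and is only being conducted at Stanford". It does not mention 68, dropout or prevalence.
- **Section 3.1.1** admits any "Patient scheduled for MR-US fusion prostate biopsy or radical prostatectomy". Cancer of a given grade is not required.
- **Section 9.1** words the primary outcome in terms of high-grade (Gleason ≥7) foci, judged against prostatectomy or biopsy pathology. Section 9.2 also plans an evaluation of Gleason 6 foci.
- **Section 10.4.1** gives the primary analysis population as "The entire cohort".
- **Section 10.1** says "This study is primarily exploratory, with the goal of collecting the initial correlative data", and disclaims a direct comparison with standard of care.

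**The concern.** Sensitivity is a proportion among those who have the target condition. Counted per patient, its denominator is the men with Gleason ≥7 on reference pathology, not everyone who is imaged. Section 10.6 attaches the power to a "sample size of 68 subjected recruited", with no allowance for men whose pathology proves benign or Gleason 6. The plan nowhere says what share will be positive.

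Two further gaps make the statement impossible to verify. The analysis unit is open, because 9.1 speaks of foci while 10.6 counts subjects. The enrolment is also open, because 10.6 says 68 and 10.7 says 100 with no link between them.

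At stake is whether a reader can rely on the 80%, and how precisely sensitivity will be estimated in a study whose purpose is to plan larger ones.

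**Working it through.** **Inputs from the documents.** Sensitivities 90% and 77%, alpha 0.05, power 80%, 68 recruits (all 10.6); 100 participants (10.7).

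**Inputs that had to be assumed.** Test, sidedness, the roles of 77% and 90%, a per-patient unit, and a Gleason ≥7 share of 40% to 80%. The documents give none of these.

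**1. Reproducing 68.** One-sample test, null 0.77, alternative 0.90, two-sided 0.05, normal approximation:

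n = [1.96·√(0.77·0.23) + 0.8416·√(0.90·0.10)]² / 0.13² = [0.8248 + 0.2525]² / 0.0169 = 68.7, so 69.

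Power with 68 positives = Φ[(0.13·√68 − 0.8248)/0.30] = Φ(0.824) = 79.5%. The exact binomial test gives 76.3%. The plan's figure is therefore reproduced if all 68 men are positive.

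**2. Other readings of the same inputs.**

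| Reading | n |
|---|---|
| One-sided 0.05, null 0.77 | 52.8 |
| Two-sided, null 0.90 against 0.77 | 52.5 |
| Arcsine, two-sided | 61.6 |
| Two independent samples | 127 per group |
| Paired (McNemar), total discordance 13% / 15% / 20% | 58.0 / 67.3 / 90.5 |

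The paired test gives 68 only with a discordance of about 15%, which the plan does not state. It too would count reference-positive men.

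**3. Power when only some recruits are positive.** The number of positives k is Binomial(N, share), so

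Power = Σₖ Binomial(k; N, share) × Φ[(0.13·√k − z·√(0.77·0.23))/√0.09], with z = 1.96 (two-sided) or 1.645 (one-sided).

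| Assumed share Gleason ≥7 | 68 recruits, two-sided | 100 recruits, two-sided |
|---|---|---|
| 40% | 31% | 49% |
| 50% | 41% | 62% |
| 60% | 51% | 73% |
| 70% | 59% | 81% |
| 80% | 67% | 87% |

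With 100 recruits, power reaches 80% from a share of about 69% (about 72% with the exact binomial test).

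The one-sided reading needs 53 positives, so it does not explain 68. It is more favourable: 68 recruits give 58%, 75% and 81% at shares of 50%, 70% and 80%, and 100 recruits reach 80% from a share of about 53%.

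**4. Precision.** 95% half-width around 90% = 1.96·√(0.09/k):

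| Positives k | Half-width (points) |
|---|---|
| 34 (68 recruits at 50%) | ±10.1 |
| 50 (100 recruits at 50%) | ±8.3 |
| 60 (100 recruits at 60%) | ±7.6 |
| 68 (all of 68) | ±7.1 |

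**5. Per focus.** No figure can be computed, because foci per man and within-man correlation are not given.

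**The case against.** - **No arithmetic slip.** This stands: 68 is a correct count for the two-sided one-sample test. The fault is that the count is attached to recruits.
- **The power figures rest on assumptions.** This also stands, and the results vary widely with the share and the sidedness. They illustrate the gap and do not predict the power. But no share short of nearly all recruits gives 80% with 68 under the two-sided reading that reproduces the number.
- **The outcome is worded in foci.** One man can contribute several positive foci, so positives need not be fewer than recruits. Clustering within men would work in the opposite direction. This limits the numerical result to the per-patient reading, and it shows that the unit has to be stated.
- **100 may already be 68 inflated for prevalence.** 68/0.68 = 100, and men already selected for fusion biopsy or prostatectomy could plausibly have a high share. The plan does not say this, however, and 10.6 ties its power to 68 recruited. If it was the intent, one sentence settles it.
- **The study is exploratory.** Section 10.1 says so, 10.4 describes data collection without a hypothesis test, and the criteria in 10.8 concern co-registration, visual review and ROC analysis. This lowers the consequence: nothing is biased and no decision depends on the test. It does not remove an explicit power claim for the primary outcome.

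**Conclusion.** The concern holds. As written, 10.6 promises "to reach 80% power at alpha level of 0.05" from a number of recruits, while the calculation that yields that number needs the same number of men with Gleason ≥7 disease. Under the per-patient, two-sided, one-sample reading, power with 68 recruits runs from 31% to 67% over assumed shares of 40% to 80%. With 100 recruits it runs from 49% to 87%. Whether 100 is enough turns on a share the plan does not give.

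The test and unit are inferred and the share is assumed, so confidence in the size of the shortfall is moderate. That the statement is under-specified, and that 68 and 100 are not reconciled, needs no assumption. The practical effect is modest: a misleading power statement, and a half-width nearer ±8 to ±10 points than ±7 if about half the men are positive. It should be corrected.

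**What to change.** In 10.6, state the test, sidedness, null value and analysis unit (patient or focus). Then choose one of two routes.

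1. **If a test is intended** on the per-patient, one-sample, two-sided reading, write: *69 patients with Gleason ≥7 on reference pathology give 80% power to show that a true sensitivity of 90% differs from 77%.* Add the assumed share, say whether planned enrolment is 68 or 100 so that 10.6 and 10.7 agree, and restate the power and 95% half-width which that enrolment delivers. For example, 100 recruits at a 60% share gives about 60 positives, 73% power and ±7.6 points. Because the 77% is tied to PI-RADS, this route should also be squared with the statement in 10.1 that no direct comparison is intended.
2. **If no test is intended**, replace the power sentence with the expected half-width at the planned enrolment and assumed share. This fits 10.1 better.

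In 10.4.1, keep the present population and add: *Sensitivity is computed among imaged patients with Gleason ≥7 on reference pathology.*

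The cost is protocol wording only; no extra enrolment is required. On the first route, the stated power becomes less favourable unless 100 are enrolled and about 69% or more have Gleason ≥7 disease.

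### Section 10.6: the 80% power at N=68 is a normal-approximation figure; it is 76% or 86% depending on an unstated test, and requires all 68 men to have Gleason ≥7 cancer

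*Combined protocol and SAP*

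**What the plan says.** Section 10.6 of the combined protocol and SAP is headed "Statistical Power for N=68". It gives two sensitivities for significant cancer: "With earlier published data with a sensitivity of 90%, we project to" and, continuing, "detect significant cancer at a sensitivity of 77% by PIRADS 4 and 5 at Stanford". It then concludes "we propose a single micro-ultrasound cohort with a sample size of 68 subjected recruited", "to reach 80% power at alpha level of 0.05".

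The section does not say which sensitivity is the null and which the alternative, whether alpha is one- or two-sided, which test is meant, how many detections would count as success, or whether the power is approximate or exact. Section 10.4 (Primary Analysis) names no test either.

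Three other places bear on the figure:
- Section 9.1 defines the target as Gleason score ≥7.
- Section 3.1 admits men scheduled for fusion biopsy as well as men scheduled for prostatectomy.
- Section 10.7 gives a different number: "This research study is looking for 100 participants and is only being conducted at Stanford".

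**The concern.** The power statement is the only quantitative support for the sample size. Two features make it doubtful.

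First, a large-sample formula ignores the steps of the binomial distribution. At a fixed n of 68, success means reaching a whole number of detections, and moving that number by one shifts power by about ten points. If the plan does not say which number applies, the reader cannot tell which power it has or which result would count as success.

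Second, the calculation treats recruited men as the denominator of a sensitivity. A man without Gleason ≥7 cancer contributes nothing to that denominator. At stake is whether the study has anything like a four-in-five chance of showing a sensitivity of 90% to be better than 77%.

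**Working it through.** **Inputs.** From section 10.6: N = 68, power 80%, alpha 0.05, sensitivities 0.90 and 0.77. Assumed, because not stated: null p0 = 0.77, alternative p1 = 0.90, one-sample test against a fixed value (10.6 says "we propose a single micro-ultrasound cohort"), two-sided alpha, and the man rather than the focus as the unit.

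**1. The plan's own figure.** Score form of the one-sample normal approximation:

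n = [z(0.975)·√(p0(1−p0)) + z(0.80)·√(p1(1−p1))]² / (p1−p0)²

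= [1.96·√(0.77·0.23) + 0.8416·√(0.90·0.10)]² / 0.13²

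= [0.8248 + 0.2525]² / 0.0169 = 68.67

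This is 69 rounded up and 68 truncated. Power at 68:

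Φ{(0.13·√68 − 0.8248) / 0.3} = Φ(0.824) = 79.5%

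So the plan's figure reproduces as an approximation. Other readings miss 68:

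| Reading | n |
|---|---|
| One-sided score | 53 |
| Roles of 0.77 and 0.90 reversed, two-sided | 53 |
| Two-sided arcsine | 62 |
| One-sided, null variance | 65 |
| Two-sided score with continuity correction | 77 |
| Two-sided, null variance | 83 |
| Two-sample | 127 per arm |

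**2. Actual power at 68.** The score statistic is z = (x/68 − 0.77) / √(0.77·0.23/68). Tail probabilities are from Binomial(68, p).

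| | 59 of 68 | 60 of 68 |
|---|---|---|
| Score z | 1.913 | 2.202 |
| Doubled-tail exact p | 0.066 | 0.030 |
| Minimum-likelihood exact p | 0.060 | 0.030 |
| Clopper-Pearson lower limit | 0.764 | 0.781 |
| Wilson lower limit | 0.767 | 0.785 |
| P(X ≥ x) at 0.77 | 0.0328 | 0.0150 |
| P(X ≥ x) at 0.90 (power) | 86.1% | 76.3% |

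For every test in this table 59 is not significant and 60 is, so power is 76.3%. The score-ordered and Blaker exact tests have the same cut-off.

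**3. Tests with a different cut-off.** These reject at 59, with 86.1% power: the exact test ordered by likelihood ratio (p = 0.0474), mid-P (p = 0.0478), Wald (true two-sided size 0.0474), the asymptotic likelihood-ratio test (true size 0.060), and the one-sided score or exact test at 0.05 (tail 0.0328).

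**4. Power by number of cancer-positive men.** Equal-tailed exact test, at most 0.025 in the upper tail:

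| Positive men | Detections needed | Power |
|---|---|---|
| 65 | 57 | 80.1% |
| 68 | 60 | 76.3% |
| 71 | 62 | 83.1% |
| 75 | 66 | 78.6% |
| 76 | 66 | 86.5% |
| 100 | 86 | 92.7% |

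Power moves in a sawtooth. It first reaches 80% at 65 and is at or above 80% for every number from 76 to 159, the range checked.

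**5. The denominator.** The documents give no prevalence of Gleason ≥7 cancer, so the first column below is an assumed range. The 68-recruited and 100-recruited columns use the rule of step 4; the last column uses a one-sided exact test at 0.05.

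| Assumed positive | Of 68 | Power | Of 100 | Power | Of 68, one-sided 0.05 |
|---|---|---|---|---|---|
| 80% | 54 | 70.7% | 80 | 82.7% | 83.2% |
| 60% | 41 | 40.3% | 60 | 75.2% | 60.8% |
| 40% | 27 | 23.3% | 40 | 42.3% | 48.5% |

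**The case against.** The strongest reply is that the plan's arithmetic is sound: the standard approximation gives 79.5%, which rounds to 80%, and using an approximate power is ordinary practice. That stands. A reader might infer a calculation error from the 76%; the documents do not support that, because the gap comes from truncating 68.67 and from discreteness.

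Nor does every test give 76%. A reader might infer that all exact tests need 60 detections, or that only a Wald test accepts 59. Both are untrue, as step 3 of the working shows. Since 10.6 states neither test nor sidedness, 86% cannot be ruled out. Against this, a one-sided score formula gives 53, so it does not explain why 68 was chosen.

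A reader might also take 76% as the most the design can deliver, on the view that men without cancer can only lower it. That fails too: 65 positive men give 80.1%, and 10.7 plans 100 participants, so 68 is not clearly the largest possible number of positives. One could suppose that 100 are recruited in order to yield 68 positives, but 10.6 describes 68 as the number recruited and nothing links the two figures.

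Finally, section 10.1 calls the study primarily exploratory and disclaims a direct comparison with standard of care, and section 10.8 rests later studies on visual feedback and an initial ROC analysis. No decision in the plan turns on 59 versus 60 detections. This lowers the stakes, but 10.6 still makes a formal power claim, and it should be one that a reader can verify.

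**Conclusion.** The concern holds in a limited form. The stated 80% is an approximation. Under the test whose formula yields 68, and under the Clopper-Pearson and usual two-sided exact tests, actual power is 76.3%, which is 3.7 points lower; the chance of missing a true 90% sensitivity is then 24% rather than 20%. Under other tests that the wording does not exclude, it is 86.1%.

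The denominator is potentially the larger problem. Both figures require every one of the 68 men to have Gleason ≥7 cancer, which eligibility does not secure. At the assumed prevalences of 80%, 60% and 40%, equal-tailed exact power falls to about 71%, 40% and 23%; a one-sided test at 0.05 falls to 61% and 48% at the two lower ones.

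The conclusion rests on 0.77 as null and 0.90 as alternative, a one-sample comparison with a fixed value, and a per-man analysis. Two-sided alpha is inferred from N = 68, not stated. It is worth correcting because the plan's sample size depends on it and the correction is small.

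**What to change.** Restate section 10.6 with null sensitivity 0.77, alternative 0.90, and a two-sided exact binomial test at 0.05. Name the equal-tailed (Clopper-Pearson) version, since exact tests differ in their cut-offs. Express power per number of men with Gleason ≥7 cancer rather than per man recruited: 76% with 68 such men (60 detections needed), and at or above 80% for every number from 76 upward within the range checked.

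Reconcile 68 with the 100 participants in section 10.7. If 100 is the intended recruitment, state that 80% power holds provided at least 76 of the 100 have Gleason ≥7 cancer, and give the expected proportion so that the condition can be judged.

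The cost is a sentence or two. No patients are added; the stated power at 68 becomes slightly less favourable, and its dependence on cancer-positive men becomes visible.
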